# LIST OF ABBREVIATIONS

Abbreviation /Acronym	Term
ACD	Anterior Chamber Depth
ADE	Adverse Device Effect
AE	Adverse Event
AL	Axial Length
BCDVA	Best Corrected Distance Visual Acuity
BCNVA	Best Corrected Near Visual Acuity
BfArM	Federal Institute for Drugs and Medical Devices (Bundesinstitut für Arzneimittel und Medizinprodukte)
BSS	Balanced Salt Solution
CE	Conformité Européene
CECC	Corneal Endothelial Cell Count
CIP	Clinical Investigation Plan
CRF	Case Report Form
CRO	Contract Research Organization
CTS	Clinical Trial Suite
D	Diopter
DCIVA	Distance Corrected Intermediate Visual Acuity
DCNVA	Distance Corrected Near Visual Acuity
DOA	Delegation of Authority
EC	Ethics Committee
ECD	Endothelial Cell Density
EDOF	Extended Depth of Focus
eQMS	Electronic Quality Management System
ETDRS	Early Treatment Diabetic Retinopathy Study
EU	European Union
FAS	Full Analysis Set
FMEA	Failure Mode Effects Analysis
FTP	Foam Tip Plunger
GCPs	Good Clinical Practices
HEMA	Hydroxyethylmethacrylate
НОА	Higher Order Abberrations
ID	Identification
ICF	Informed Consent Form
ICH	International Conference on Harmonisation/ Implantable Collamer® Lens for Hyperopia
ICL	Implantable Collamer® Lens
ICM	Implantable Collamer® Lens for Myopia
IOL	Intraocular Lens

Abbreviation /Acronym	Term
ISO	International Organization for Standardization
LASIK	Laser Assisted In Situ Keratomileusis
MeDRA	Medical Dictionary for Regulatory Devices
MPG	Medical Devices Act- Germany
MPSV	German Safety Plan for Medical Devices (Medizinproduktesicherheitsverordnung)
MRSE	Manifest Refractive Spherical Equivalent
OCT	Optical Coherence Tomography
PI	Principal Investigator/ Peripheral iridotomy/iridectomy
pIOL	Phakic Intraocular Lens
PPS	Per Protocol Set
PT	Preferred Term
SADE	Serious Adverse Device Effect
SAE	Serious Adverse Event
SAP	Statistical Analysis Plan
SD	Standard Deviation
SE	Spherical Equivalent
SES	Safety Evaluation Set
SOC	Standard of Care/System Organ Class
SOP	Standard Operating Procedure
SPK	Superficial Punctate Keratitis
UCDVA	Uncorrected Distance Visual Acuity
UCIVA	Uncorrected Intermediate Visual Acuity
UCNVA	Uncorrected Near Visual Acuity
US	United States
USADE	Unanticipated Serious Adverse Device Effect
UV	Ultraviolet
VA	Visual Acuity
VICH6	STAAR EVO+ Visian ™ Implantable Collamer® Lens (VICL) with Aspheric (EDOF) Optic for hyperopia
VICL	Visian ™ Implantable Collamer ® Lens
VICM6	STAAR EVO+ Visian ™ Implantable Collamer® Lens (VICL) with Aspheric (EDOF) Optic for myopia

NOTE: The first occurrence of some abbreviations is not spelled out in the document (eg, units of measure).

# SYNOPSIS

STAAR Surgical Company Study #CP17-01		
Revision chronology:	Rev 01, 2017.11.09 Rev 02, 2018.01.19 Rev 03, 2018.01.30 Rev 04, 2018, 08.14	
Title:	A Multicenter Clinical Evaluation of the Clinical Performance of a Phakic Intraocular Lens	
Type of study:	Performance	
Objective(s):	The objective of this clinical study is to evaluate the clinical performance of the STAAR EVO+ Visian ™ Implantable Collamer® Lens (VICL) with Aspheric (EDOF) Optic [EDOF ICL] in improving uncorrected near visual acuity (UCNVA).	
Study design:	This prospective, open-labeled, evaluation of clinical performance of the CE-Marked EDOF ICL for the improvement of UCNVA will be conducted at approximately 6 clinical sites in Europe. Approximately 48 subjects who meet all eligibility criteria will undergo phakic IOL implantation in both eyes.	
	Postoperatively, subjects will undergo ophthalmic examination at regular intervals per the study visit schedule up to 6 months after surgery.	
Inclusion criteria:	1. Subjects must be able to read, understand and provide written informed consent on the Ethics Committee (EC) approved Informed Consent Form (ICF) and provide authorization as appropriate for local privacy regulations,	
	2. Willing and able to comply with all treatment and follow-up study related procedures,	
	
 
Subjects who require a spherical lens power from -0.50 D to -18.00 D must be 40 - 60 years of age at time of surgery,
 
	
	4. Subjects who require a spherical lens power from 0.0 D to +3.00 D must be 35 – 45 years of age at time of surgery,	
	5. Preoperative refraction that can be fully corrected (target emmetropia) with available ICL powers, with $\leq 0.75$ D preoperative refractive and residual cylinder,	
	6. Must have less than 0.75 D spherical equivalent (SE) difference between cycloplegic and manifest refractions,	
	
 
Must have a stable correction (± 0.50 D) as determined by manifest refractive spherical equivalent (MRSE) from consecutive refractions, medical records, or prescription history,
 
	
	8. Best Corrected Distance Visual Acuity (BCDVA) 20/20 or better in both eyes,	
	9. Requires +1.00 D to +2.50 D reading add,	
	10.	

	STAAR Surgical Company Study #CP17-01
	11. ACD $\geq$ 2.8 mm as measured from the corneal endothelium to the anterior lens capsule for subjects who require a spherical lens power from -0.50 D to -18.00 D
	12. ACD $\geq$ 3.0 mm as measured from the corneal endothelium to the anterior lens capsule for subjects who require a spherical lens power from 0.0 D to +3.00 D,
	13. Anterior chamber angle $\geq$ Grade III,
	14. Phakic in both eyes,
	15. Current contact lens wearers need to demonstrate a stable refraction, (± 0.5 D), expressed as MRSE, on two consecutive examination dates with refractive stability determined by the following criteria:
	
 
a. contact lenses were not worn for at least 2 weeks (rigid and toric contact lenses) or 3 days (soft contact lenses) prior to the first refraction,
 

	b. two refractions were performed at least 7 days apart.
Exclusion criteria:	1. Participation in a clinical trial within 30 days prior to entry into this study and/or during the period of study participation,
	2. Previous intraocular or corneal surgery in either eye, including refractive surgery (e.g., LASIK),
	3. Progressive sight threatening disease or other previous or current ocular conditions, other than myopia, that may predispose for future complication (e.g., diabetic retinopathy, pseudoexfoliation, retinal detachment, ocular hypertension or glaucoma, clinically significant corneal disease (Fuchs, keratoconus, herpes simplex or zoster keratitis), retinal vascular disease, cataract, etc.) in either eye,
	4. Low/abnormal corneal endothelial cell density (ECD) according to recommendations in ISO-11979-10 (Tab. A.1),
	5.
	6. Amblyopia,
	
 
Presence of active or history of chronic inflammation in either eye (e.g., scleritis, uveitis, etc.),
 

	8. Clinically significant irregular astigmatism in either eye, as determined by the Investigator,
	9. Serious (i.e., life threatening), acute, chronic or systemic, non- ophthalmic disease or illness that would increase the operative risk, confound the outcome(s) of the study or which may preclude study completion (e.g., immunocompromised, connective tissue disease, clinically significant atopic disease, uncontrolled diabetes, insulin dependent diabetes, etc.),
	10. Use of topical steroids at time of implantation,
	11. Systemic or topical medication, other than prescribed study medications (e.g., systemic corticosteroids, anti-metabolites) that may confound the outcome or increase the risk to the subject,

STAAR Surgical Company Study #CP17-01		
	12. Allergy to anesthetics or other postoperative medications required in this study,	
	13. Subject who is pregnant, plans to become pregnant, or is lactating during the course of the study, or has another condition associated with the fluctuation of hormones that could lead to refractive changes,	
	14. Subjects who, in the judgment of the Investigator, present any emotional, physiologic, or anatomical condition which may preclude participation in this study or provide an inappropriate landscape for the intended study treatment.	
Investigational device:	The EDOF ICL includes a refractive optic and features a single piece lens design with a convex/concave optic zone of 4.9 to 6.1 mm diameter (according to model and power) and a 0.36 mm diameter central hole in the optic known as the KS-AquaPORT®. The lens is manufactured in five overall diameters: 11.6, 12.1, 12.6, 13.2, and 13.7 mm to accommodate different eye sizes. The lens is manufactured from Collamer, a proprietary polymer made from collagen, hydroxyethylmethacrylate (HEMA) and an ultraviolet (UV) absorber. The 10% UV cut-off for the ICL is at 387 nm wavelength. The lens is supplied with a delivery system for implantation through an incision of 3.5 mm or less.	
Study endpoints:	Performance Endpoints	
	Primary performance endpoint:	
	• Achievement of monocular UCNVA of Snellen equivalent 20/40 or better at 40 cm at Visit 5 (6 months after implantation) in equal to or greater than 75% of implanted eyes (responder rate)	
	Secondary performance endpoints include the following:	
	• Percentage of implanted eyes achieving monocular UCNVA of Snellen equivalent 20/40 or better at 40 cm at Visit 3 and 4 (1 and 3 months after implantation respectively)	
	• Change from baseline in monocular uncorrected intermediate visual acuity (UCIVA) at 80 cm at postoperative Visit 3, 4 and 5	
	• Change from baseline in monocular UCNVA at 40 cm at postoperative Visit 3, 4 and 5	
	• Change from baseline in monocular distance corrected intermediate visual acuity (DCIVA) at 80 cm at postoperative Visit 3, 4 and 5	
	• Change from baseline in monocular distance corrected near visual acuity (DCNVA) at 40 cm at postoperative Visit 3, 4 and 5	
	• Change from baseline in binocular UCNVA at 40 cm at postoperative Visit 3, 4 and 5	
	There are no prespecified performance targets for the secondary performance endpoints.	
	Safety Endpoint	
	• Ocular adverse event (AE) rates assessed in implanted eyes	
	There are no prespecified performance targets for the safety endpoint.	
Statistical methods:	The primary performance endpoint is defined as achievement of monocular UCNVA of Snellen equivalent 20/40 or better at 40 cm at Visit 5 (6 months after implantation) in equal to or greater than 75% of implanted eyes (responder rate). The analysis will be performed on all	

STAAR Surgical Company Study #CP17-01		
	eyes.	
	The implant procedure is defined as successful if the responder rate is equal to or greater than 75%. The corresponding statistical hypothesis is therefore as follows:	
	H 0 (null hypothesis): $\pi < 0.75$	
	H a (alternative hypothesis): $\pi \ge 0.75$	
	where $\pi$ is the true proportion of eyes that achieve the performance endpoint at 6 months postoperative (6-month responder rate). Fleming's two-stage design was used to optimize the sample size while allowing for early termination due to rejecting the null hypothesis. It is expected that 90% of eyes will achieve the performance endpoint and the sample size was therefore conservatively determined based on an 87.5% responder rate.	
	In the first stage, 27 patients (54 eyes) will be evaluated. If there are 43 or less response the trial will be stopped for futility since the likelihood of still obtaining a significant result is too low to continue the study under ethical considerations. If there are 48 or more responses the trial will be stopped and the null hypothesis rejected as enough statistical evidence has been accrued to determine that, within the certainty of the controlled one-sided type I error probability of 2.5%, the true responder rate is not lower than 75%.	
	Otherwise, 16 additional patients (32 eyes) will be recruited for a total of 43 patients (86 eyes). The null hypothesis will be rejected if 73 or more responses are observed among the 86 eyes. This design yields a one-sided type I error probability of 2.5% and a power of 80% if the true response rate is 87.5%.	
	Summaries for continuous variables will include the number of non- missing observations, mean, standard deviation (SD), median, minimum, and maximum. Summaries for discrete variables will include the tabulation of frequencies and percentages.	

# **1.0** INTRODUCTION

The STAAR Implantable Collamer® Lens (ICL) first obtained approval in 1997 for the original ICH (for hyperopia) and ICM (myopia) lens models. Since the approval of the first ICL, incremental improvements and expansion in the technology have been brought to patients globally. The ICL has a substantial history of clinical effectiveness while presenting a favorable safety profile with over 700,000 ICLs implanted globally.

The STAAR EVO+ Visian™ Implantable Collamer® Lens (VICL) with Aspheric (EDOF) Optic (models VICH6 and VICM6 [EDOF ICL]) received CE Mark on May 11, 2017.

The EDOF ICL is indicated for use in phakic eye treatment in adults with an anterior chamber depth (ACD) equal to or greater than 3.0 mm, as measured from the corneal endothelium to the anterior lens capsule, and:

1. 21- 60 years of age for the correction/reduction of myopia in adults ranging from -0.5 D to -20.0 D at the spectacle plane.

Or

2. 21-45 years of age for the correction/reduction of hyperopia in adults ranging from +0.5 D to +16.0 D at the spectacle plane.

The EDOF ICL models include a combination of the most advanced elements of the ICL platform, an increased diameter of the optic to accommodate larger pupils and the center port (KS-AquaPORT®) allowing for implantation without the need of peripheral iridotomies/iridectomies (PIs). These features are combined with asphericity, the addition of hyperfocal optics utilizing circularly-symmetric Zernike polynomial aberrations (to 8,0). The added aspheric optic is designed to provide extended depth of focus (EDOF).

The ICL is intended to be implanted within the posterior chamber, directly behind the iris, and in front of the anterior capsule of the human crystalline lens. It offers an intraocular alternative for the correction of refractive error in those who currently utilize spectacle and/or contact lenses correction. Other alternative refractive surgical procedures include: excimer laser surgery (including photorefractive keratectomy (PRK) and laser assisted in situ keratomileusis (LASIK)), radial keratotomy (RK), automated lamellar keratectomy (ALK), epikeratoplasty, intracorneal implants (lenses or rings), anterior chamber and sulcus-placed phakic intraocular lenses (pIOLs), refractive lens exchange, and combinations of two or more of these procedures.

Presbyopia is a condition associated with the expected age-related decline in near-focusing ability that becomes manifest at approximately age 45. Presbyopia affects all people, regardless of their underlying refractive error. Those who are farsighted prior to the onset of presbyopia will likely experience difficulty with near vision at a somewhat younger age, while those who are nearsighted may not notice the onset of presbyopia until somewhat later. Regardless, all people will eventually require optical correction in addition to any distance correction for near vision tasks such as reading.

Presbyopia is associated with reduced health-related quality of life, and presbyopia corrected with glasses is associated with a nominal decrease in quality of life, similar to that of treated systemic hypertension. Approximately 10% of presbyopic patients suffer such inconvenience from spectacle correction that they would consider surgical intervention.

Individuals who have had refractive surgery such as LASIK for correction of their distance vision will still experience presbyopia when they reach their mid-forties. Monovision, the intended correction of one eye for near vision and the fellow eye for distance vision, represents a common strategy for addressing presbyopia in older patients undergoing LASIK. Intraocular lens (IOL) implants intended for use at the time of cataract surgery have also been used to provide monovision. While monovision correction of presbyopia is related to some improvements in health-related quality of life, the quality of life with monovision is still worse than the quality of life for younger subjects with emmetropia. Specific presbyopia-correcting IOLs have also been developed incorporating multifocal and EDOF optical elements intended to provide simultaneous vision at near and far distances. While monovision LASIK, multifocal IOLs and corneal implants have been developed to improve near vision, these methods typically result in some expected degradation of distance vision and unwanted optical side effects such as halos and glare in order to gain an improvement in uncorrected near vision.

# 1.1 Clinical and Non-clinical Information

Preclinical bench-testing conducted by STAAR has demonstrated that the STAAR EVO+ Visian Implantable Collamer Lens (VICL) with Aspheric (EDOF) Optic [EDOF ICL] demonstrates at least 1.5 D of field depth with acceptably high image quality (20/20) both at distance focus and throughout the depth of field.

# 1.2 Hypothesis

The implant procedure is defined as successful if the responder rate is equal to or greater than 75%. The corresponding statistical hypothesis is therefore as follows:

H 0 (null hypothesis):	$\pi < 0.75$
H a (alternative hypothesis):	$\pi \ge 0.75$

where  $\pi$  is the true proportion of eyes that achieve the performance endpoint (i.e., uncorrected near visual acuity (UCNVA) of Snellen equivalent 20/40 or better at 40 cm) at 6 months after implantation (6-month responder rate).

# 2.0 OBJECTIVE

The objective of this clinical study is to evaluate the clinical performance of the STAAR EDOF ICL in improving UCNVA.

# 3.0 STUDY DESIGN

#### 3.1 Description of Study Design

This is a prospective, open-labeled, multi-site evaluation of clinical performance of the CE-Marked EDOF ICL for the improvement of UCNVA. Approximately 48 subjects who meet all eligibility criteria will undergo phakic IOL implantation in both eyes. All eyes will be followed for 6 months after surgery.

The first eye implanted with the study lens and the appropriate time for fellow eye implantation will be determined by the medical judgement of the Investigator. All eyes will be analyzed for safety and performance.

The subject will have completed the entire study when the study lenses have been implanted bilaterally and the Sponsor receives completed case report form (CRF) documentation for all visits. A Study Exit CRF for each eye must be completed for all subjects enrolled in the study.

# 3.2 Selection of Study Population

A total of up to 48 subjects (96 eyes) at approximately 6 clinical sites in the EU who meet all eligibility criteria will be offered enrollment into this study.

#### 3.2.1 Eligibility

# 3.2.1.1 Inclusion Criteria

This study will include subjects who meet the following criteria:

- Subjects must be able to read, understand and provide written informed consent on the Ethics Committee (EC) approved Informed Consent Form (ICF) and provide authorization as appropriate for local privacy regulations,
- 2. Willing and able to comply with all treatment and follow-up study related procedures,

- 3. Subjects who require a spherical lens power from -0.50 D to -18.00 D must be 40 60 years of age at time of surgery,
- 4. Subjects who require a spherical lens power from 0.0 D to +3.00 D must be 35 45 years of age at time of surgery,
- 5. Preoperative refraction that can be fully corrected (target emmetropia) with available ICL powers, with  $\leq 0.75$  D preoperative refractive and residual cylinder,
- 6. Must have less than 0.75 D spherical equivalent (SE) difference between cycloplegic and manifest refractions,
- Must have a stable correction (± 0.50 D) as determined by manifest refractive spherical equivalent (MRSE) from consecutive refractions, medical records, or prescription history,
- 8. Best Corrected Distance Visual Acuity (BCDVA) 20/20 or better in both eyes,
- 9. Requires +1.00 D to +2.50 D reading add,
- 10.
- 11. ACD  $\ge$  2.8 mm as measured from the corneal endothelium to the anterior lens capsule for subjects who require a spherical lens power from -0.50 D to -18.00 D,
- 12. ACD  $\ge$  3.0 mm as measured from the corneal endothelium to the anterior lens capsule for subjects who require a spherical lens power from 0.0 D to +3.00 D,
- 13. Anterior chamber angle  $\geq$  Grade III,
- 14. Phakic in both eyes,
- 15. Current contact lens wearers need to demonstrate a stable refraction,

 $(\pm 0.5 \text{ D})$ , expressed as MRSE, on two consecutive examination dates with refractive stability determined by the following criteria:

- contact lenses were not worn for at least 2 weeks (rigid and toric contact lenses) or 3 days (soft contact lenses) prior to the first refraction,
- two refractions were performed at least 7 days apart.

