#### 4.7 Risk Assessment

The EVO+ EDOF ICL has been assessed for risk control measures per established risk analysis and FMEA reports. The use of CE-Marked model in the context of this clinical study requires the residual risk to be balanced against the anticipated benefit of the procedure. The risk level has been determined to be in the lowest category, deeming the risk to be acceptable, and it is believed that the benefits outweigh any of the identified or associated residual risks with this clinical evaluation.

If new information regarding new risks to patients is made available during the course of the study, the EC and applicable regulatory agencies will be notified, the informed consent will be updated and the Investigator will be required to provide new information to patients and have them sign the revised ICF.

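### Inclusion criterion 11 permits minus-power eyes with an anterior chamber depth from 2.8 mm, but the indication quoted in Section 1.0 starts at 3.0 mm, and the protocol does not acknowledge the gap

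*Combined protocol and SAP*

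**What the plan says.** Section 1.0 reports the CE mark and then gives the indication, which is for phakic eyes "in adults with an anterior chamber depth (ACD) equal to or greater than 3.0 mm, as measured from the corneal endothelium", with the anterior lens capsule as the other end point. Two branches follow. The myopia branch covers ages 21 to 60, "years of age for the correction/reduction of myopia in adults ranging from -0.5 D to -20.0 D at the spectacle plane"; the hyperopia branch has its own age and power range. Neither branch carries a depth limit of its own.

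The eligibility criteria set the limit by lens power. Criterion 11 in Section 3.2.1.1 requires at least "2.8 mm as measured from the corneal endothelium to the anterior lens capsule" when the lens power needed lies between -0.50 D and -18.00 D, and the Synopsis gives the same figure. Criterion 12 requires at least "3.0 mm as measured from the corneal endothelium to the anterior lens capsule for subjects who require a spherical lens power from 0.0 D" up to +3.00 D.

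Section 3.1 presents the study as an evaluation of the CE-marked lens. Section 4.7 weighs residual risk in terms of using the CE-marked model and concludes: "The risk level has been determined to be in the lowest category". It does not mention anterior chamber depth (ACD).

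**The concern.** The conflict is over a threshold that decides who may be implanted. A site that follows criterion 11 can enrol a subject whom the protocol's own introduction places outside the indication. An ethics committee or investigator reading Sections 1.0 and 4.7 would not learn this, because both speak of the CE-marked lens without qualification.

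The planned safety output would not bring these eyes into view either. Section 7.5 summarises adverse events by system organ class, preferred term, intensity and relationship to the lens. Its listings cover serious events, deaths and ocular events leading to discontinuation. Section 7.4 plans no subgroup analysis. Nothing is broken down by ACD.

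**Working it through.** No sample-size or error-rate formula applies, so the check sets the passages side by side.

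| Place | Applies to | Minimum ACD | Measured between |
|---|---|---|---|
| Section 1.0, indication | Myopia and hyperopia | 3.0 mm | Corneal endothelium and anterior lens capsule |
| Criterion 11 (Synopsis, 3.2.1.1) | Lens power -0.50 D to -18.00 D | 2.8 mm | Same |
| Criterion 12 (Synopsis, 3.2.1.1) | Lens power 0.0 D to +3.00 D | 3.0 mm | Same |
| Section 4.7, risk | CE-marked model | Not mentioned | Not applicable |
| Appendix C, ACD | All preoperative measurements | None set | Posterior corneal surface and anterior crystalline lens surface |

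1. *Size of the gap.* For minus powers, 3.0 - 2.8 = 0.2 mm. For 0.0 D to +3.00 D, 3.0 - 3.0 = 0, so the conflict is confined to criterion 11.

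2. *Eyes concerned.* Appendix C records ACD in mm to two decimals. The band that is eligible but outside the quoted indication is therefore 2.80 to 2.99 mm in minus-power subjects.

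3. *Could it be a difference in measurement?* No. Section 1.0 and criterion 11 name the same two surfaces, and the Appendix C definition is the same distance, since the endothelium is the posterior surface of the cornea.

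4. *Could it be a typing slip?* That is unlikely. The Synopsis and the body both give 2.8 mm, and criterion 12 separately keeps 3.0 mm. The criteria distinguish the two power ranges; Section 1.0 does not.

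5. *Is it explained elsewhere?* No visible text gives a reason for 2.8 mm or acknowledges use below 3.0 mm. Inclusion criterion 10 and exclusion criterion 5 are blank in the public text and cannot be assessed.

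6. *Effect on the primary analysis.* None. The decision rules (stop at 43 or fewer or at 48 or more responses in 54 eyes; otherwise require 73 of 86), the one-sided 2.5% error rate and the 80% power at 87.5% make no use of ACD.

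**The case against.** The strongest reply is that sites face no ambiguity. Section 1.0 is background, enrolment follows the criteria, and criteria 11 and 12 are clear and look deliberate. Studying eyes beyond a quoted indication is not in itself an error. Other anatomical screens also apply: an anterior chamber angle of Grade III or more, and the investigator's judgement under exclusion criterion 14. This stands as far as it goes. The rule is usable; what is missing is any acknowledgement that it departs from the indication quoted in the same document.

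A reader might infer more than the text supports:

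- *That the device is indicated only from 3.0 mm.* Section 1.0 says what the lens is indicated for. It does not use a word of exclusion.
- *That the risk conclusion rests on the 3.0 mm limit, or leaves these eyes out.* Section 4.7 cites risk analysis and FMEA reports that are not in the documents. They may cover eyes below 3.0 mm. One can say only that Section 4.7 is silent on ACD.
- *That the trial will implant such eyes, in some particular number.* Criterion 11 permits them; nothing shows that any will enrol. The documents give neither the distribution of ACD nor the size of the minus-power group, and the trial may stop after a first stage of 54 eyes. An assumed share multiplied by 96 eyes would only restate the assumption.
- *That subjects are not told.* The consent pages are not in the text reviewed, so nothing can be said about their wording.

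It can also be argued that an extra listing is optional, because adverse events and preoperative ACD are collected anyway. That is true of the data, but the planned output does not bring the two together.

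**Conclusion.** The inconsistency is real. Minus-power eyes from 2.80 to 2.99 mm are eligible under criterion 11 and outside the indication as Section 1.0 quotes it, and neither Section 1.0 nor Section 4.7 acknowledges this. The conclusion assumes only that the ACD condition in Section 1.0 governs both branches, as its position ahead of them indicates.

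The size is 0.2 mm in the limit; the number of eyes is unknown and not computable. No safety consequence is shown, because the documents give no reason for either limit. Confidence is high in the mismatch and does not extend to any claim about harm. The sponsor should resolve it because it concerns who is implanted and is cheap to settle.

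**What to change.** Reconcile Section 1.0, criterion 11 (Synopsis and Section 3.2.1.1) and Section 4.7 so that they state one position. Which limit is right is for the sponsor to settle; this review takes no view.

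If both limits are intended:

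- Section 4.7 should state that some eligible eyes fall outside the indication quoted in Section 1.0 and, once the underlying risk reports have been checked, that the risk assessment covers them.
- The safety output in Section 7.5 or the SAP should include a listing of ocular adverse events for implanted eyes with preoperative ACD below 3.0 mm. It is descriptive and needs no subgroup test.

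No new data are needed: Tables A1 and A2 schedule ACD before surgery for both eyes, and Appendix C has it recorded to 0.01 mm. The cost is a text amendment and one listing, with a possible small effect on recruitment depending on how the limits are reconciled.
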